1. STUDY AIM, BACKGROUND, AND DESIGN ABSTRACT

Low-income and racial/ethnic minorities suffer disproportionately from substance use disorders, evidencing consistently lower rates of critical treatment outcomes, including treatment engagement and retention¹. While these individuals exhibited a need for evidence-based care prior to the pandemic², low-income, racial/ethnic minority populations have been disproportionately affected by COVID-19³, as have persons with SUDs⁴.

Peer Recovery Coaches (PRC) are individuals with lived-experiences with substance use who have been certified by the state to assist in treatment recovery⁵. Because of similarities between PRCs and substance use clients, PRCs can overcome many of the barriers that clients face to engaging and staying in SUD treatment, such as stigma⁶. The goal of the current project is to conduct an open-label pilot trial to examine the feasibility, acceptability and accessibility of a PRC-led intervention to support retention in SUD care.

This project proposes to develop a novel and sustainable model for improving retention in SUD treatment by training PRCs to deliver an evidence-based intervention (EBI), Behavioral Activation (BA). BA seeks to increase the positive reinforcement patients experience from their natural environment by promoting prosocial and valued experiences. BA has been found to improve substance use treatment retention and adherence, as well as medication adherence in low-income individuals with HIV/AIDS. To that end, we propose the following goal: to evaluate the preliminary feasibility, acceptability, and effectiveness of the PRC- delivered BA approach. We will conduct an open-label clinical trial ($n=40$) of the adapted PRC-delivered BA intervention and training protocol in a representative agency in Detroit, MI serving a low-income, predominantly African-American population. Findings from this phase of the project will be used to re-adapt the manual and training procedures.

2. SUBJECT POPULATION AND ELIGIBILITY

The Detroit Recovery Project (DRP) is located in Detroit, Michigan. The DRP offers a variety of services to their clientele, including, though not limited to, case management, medication for opioid use disorder (MOUD), and peer recovery support. All CDC COVID-19 guidelines are practiced at the DRP. Throughout this study, patients will have the option to engage with researchers in-person at DRP and/or to perform study activities by phone or computer at their home or another private location.

All DRP visitors who are at least 18 years old, and meet criteria for a SUD will have the opportunity to learn about this study from DRP staff, and if interested, will be referred to research staff to learn more about and potentially enroll in the study. Due to variable access to communication technologies across the patient population at DRP (i.e., very limited smart phone or A/V technology access, and limited cell phone minute access), we will offer several ways for patients who have indicated their interest in participating in research to connect with our team as to not exclude individuals based upon lack of access to technology. Options include: 1) Direct communication via telephone, text messaging, or email, whereby research staff can contact eligible patients who have indicated that they are interested in research participation to ask if they are interested in hearing information about a study that is testing a new intervention to help people stay in treatment; 2) Direct in-person communication; 3) A study flyer provided to eligible individuals by DRP staff which provides space for the individual to list their name and contact details and deposit the completed flyer in a lockbox checked routinely by the study staff. Direct communication via telephone, texting, or email utilizes contact information provided to DRP by the patient. In the case that a patient does not have reliable access to their own phone,

contact information may include an emergency/alternative contact other than the patient themselves. The research team may use any contact information provided by the patient, including alternative/emergency contacts. If the research team contacts someone other than the patient, they will provide contact information for the patient to follow up or otherwise coordinate direct communication with the patient. Interested individuals will also have the opportunity to write their name and contact details on a research study flyer and to deposit this flyer in a secure lockbox for the research team to contact them or give this flyer to DRP staff.

Before engaging in any in-person research activities on-site, all enrolled participants and patients interested in the study will be screened for COVID-19 risk and will be required to wear the appropriate personal protective equipment (PPE). All visitors at DRP (including staff, patients, and visitors) are screened for COVID infection or exposure risk by the DRP staff using up-to-date protocols including temperature check. Visitors are required to wear a facemask and to pass the screener in order to gain access to the DRP building. Therefore, screening will take place for all participants. Any participant who screens positive will be excluded from in-person study engagement and will be engaged virtually.

After discussing the study with the research team member by telecommunication (audio or video) or in-person and based on continued interest, the participant will be invited to complete the informed consent process (detailed below in Procedures) and to schedule the baseline assessment. In all cases, patients will be informed that the study provides ClinCard compensation for participation (see Recruitment Script). The study team member will reiterate that participation in the study will in no way affect any services that they receive at DRP or elsewhere and will emphasize that they may participate through tele-sessions if this would work best for them or due to COVID-19 safety concerns. The study team member will also work with the participant to understand their access to technology for study communication. The study team will work with each participant to try to accommodate their individual frequency needs (aiming for a minimum of every other week) for intervention and other study-related contact, with flexibility of timing based on each individual's treatment schedule and needs. The study team will keep a record of participant access to technology (e.g. phone minutes, texting capability, video capability, WiFi, etc.) in a HFHS REDCap database (non-identifiable information only). As needed, the research team will provide information on/assistance with applying for a phone through public assistance programs and other resources available at DRP.

a. Eligibility Criteria:

Participants must (1) meet criteria for SUD; and (2) be over the age of 18.

Exclusion criteria will be (1) demonstrating active, unstable or untreated psychiatric symptoms, including mania and/or psychosis; or (2) inability to understand the study and give informed consent in English.

Active, Unstable or Untreated Psychiatric Symptoms: The study team is committed to recruiting a sample that reflects the complexity and likely comorbidity of people with moderate to severe SUD in this setting. Therefore, we will only exclude people whose concurrent mental health issues preclude ability to participate with the procedures in this study. Throughout the study, researchers will monitor for active, unstable or untreated psychiatric symptoms as the presence of these symptoms during study procedures would interfere with participation. Monitoring for exclusionary psychiatric symptoms can include reviewing data in medical chart (per protocol-approved access to medical records), observation during assessments and intervention sessions, and/or current symptoms detected on the MINI modules for psychosis and mania.

Inability to complete informed consent/ study in English. This study/intervention will be implemented in English only. Therefore, the capacity and willingness to give written informed consent in English, to understand the study and inclusion and exclusion criteria in English.

- b. **Rationale:** The DRP is a community-based, outpatient substance use resource center. The program provides SUD treatment services to adults living in the Detroit metropolitan area. The program serves many people of low-income, racial/ethnic minority patients with SUD who struggle with treatment retention. Thus, recruiting from this population is appropriate, given the aims of our study.
- c. **Enrollment Numbers:** For the open-label trial, we will enroll a maximum of 40 patients.
- d. **Rationale for Enrollment Numbers:** We will enroll up to 40 patients because we expect to have a retention rate of 80% based upon current retention rates in other research at this site. The minimum target size (n=32) is large enough to allow us to demonstrate feasibility, implementation, acceptability, and preliminary efficacy for the intervention and also allow us to make any changes to the protocol if deemed necessary prior to collecting the full sample.

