3. STUDY PROCEDURES

Recruitment and Screening:

As stated above, recruitment will take place at the Detroit Recovery Project (DRP). All patients with SUD will be given the opportunity to learn more about this study from DRP staff, who will refer patients to research staff if interested. Patients will be contacted by a member of the research study team by phone, text, email, or in-person (during routine visit to the treatment center) and asked if they are interested in hearing about a study that is testing a new intervention to help people stay in treatment. Interested individuals will also have the opportunity to write their name and contact details on a research study flyer and to deposit this flyer in a secure lockbox for the research team to contact them.

Patients will be informed that the study provides ClinCard compensation, that their participation is voluntary, and that participation has no impact on their treatment at DRP or at any other location.

All DRP patients who present with SUD are referred at intake; for new patients, a small battery of assessments will be integrated into the intake in order to assess eligibility. The baseline will then be finished by a researcher if the potential participant is eligible, interested and consents to participation. After discussing the study with a research team member, and based on patient continued interest, participants will be offered paper copies of the consent form for their records.. Eligible participants who successfully complete the informed consent process will be given a unique identification number. This number will be used in place of their name for the remainder of the study.

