For any remote call with the participant, the research team will document the participant ID number, researcher name, location of research team member, location of participant, means used (telephone or computer), start and end time, quality of call (excellent, minor issues, significant impediment), and any barriers to effective communication in RedCap. For any in-person session (assessment or intervention session), researchers will follow procedures outlined in the IRB-approved in-person human subjects protocol.

Data analysis:

Quantitative data will involve pre- to-post t-tests and will utilize multiple imputation to handle missing data if deemed appropriate and necessary.

Qualitative data will be analyzed using thematic analysis, and the coding team will iteratively develop a codebook outlining themes, sub-themes, and definitions in the transcripts. The codebook will be modified as new concepts arise.

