FOREward Together: Training Peer Recovery Coaches to Promote Retention and Adherence to
MOUD

NCT05098795

Approved Statistical Analysis Plan

Approved 7/31/2024

Data Analytic Plan

Primary Outcomes: MOUD treatment retention and feasibility of intervention delivery.

Descriptive statistics will be used to characterize the sample. MOUD retention was defined *a priori* as return visits, measured for up to 24 weeks. We will calculate the percentage of participants still enrolled in the program over this period of time. Feasibility was defined, *a priori*, as the percent of patients who agreed to participate in the intervention. We will calculate the proportion of individuals who were screened eligible to the percent that engaged in the intervention, measured at study completion.

Secondary Outcomes: Intervention acceptability and intervention fidelity

Descriptive statistics will be examined for all secondary outcomes. Intervention acceptability was defined *a priori* as the percentage of patients enrolled who attend at least 75% of scheduled sessions. Intervention fidelity was defined *a priori* as the percentage of intervention elements delivered as intended. Following fidelity coding, we will calculate the number of accurately delivered components relative to the total number of coded components among a random selection of 20% of sessions.

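### Protocol 2d says 32 patients can demonstrate preliminary efficacy, but an uncontrolled pilot alongside usual treatment can only estimate, and the SAP's percentages carry no stated intervals

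*Protocol*

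**What the plan says.** Protocol section 2d caps enrolment at 40, expects 80% to be retained, and arrives at 32. It then states: "The minimum target size (n=32) is large enough to allow us to demonstrate feasibility, implementation, acceptability, and preliminary efficacy for the intervention". The same sentence adds a formative purpose: "and also allow us to make any changes to the protocol if deemed necessary prior to collecting the full sample".

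Section 1 describes an open-label pilot of a single intervention, BA delivered by a peer recovery coach. No comparator group appears anywhere. Section 1 lists effectiveness, qualified as preliminary, among the things to be evaluated, and says of the results: "Findings from this phase of the project will be used to re-adapt the manual and training procedures".

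The only inferential method is in section 3, under Data analysis: "Quantitative data will involve pre- to-post t-tests and will utilize multiple imputation to handle missing data if deemed appropriate and necessary". No outcome, significance level or sidedness is given.

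Participants are in DRP care during the study. Section 2 says DRP's services include "case management, medication for opioid use disorder (MOUD), and peer recovery support". Section 3 says "All DRP patients who present with SUD are referred at intake", and that for new patients some eligibility measures are built into intake. Section 3 also has staff extract counselor appointments and psychosocial services from DRP charts, and section 4 refers to each participant's DRP treatment team.

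The SAP makes MOUD retention (up to 24 weeks) and feasibility its primary outcomes. For retention it says "We will calculate the percentage of participants still enrolled in the program over this period of time". For acceptability and fidelity it says "Descriptive statistics will be examined for all secondary outcomes". It mentions neither a t-test nor a confidence interval.

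**The concern.** Section 2d presents efficacy as a question of sample size. It is a question of design: without a comparator, more patients give a more precise estimate of total change, but do not show how much of it is due to BA.

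Two results could be misread. One is a significant pre-post t-test. For patients recruited as new intakes, baseline falls near the start of DRP treatment, when improvement without BA and regression to the mean are both plausible. The other is the retention percentage. Retention in treatment is what the intervention is meant to improve and is an SAP primary outcome, so a high figure could easily be taken as efficacy. Section 2d would appear to license either reading.

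Separately, these results feed the re-adaptation of the manual and training. With at most 40 patients, percentages based on enrolled patients are imprecise, and the plan does not ask for that imprecision to be shown.

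**Working it through.** **Step 1. The plan's own figure.** Inputs from Protocol section 2d: maximum enrolment 40, expected retention 80%. 40 × 0.80 = 32, and back, 32 / 0.80 = 40. The figure reproduces. No effect size, SD, significance level, power or target precision is stated, so there is nothing further to reproduce.

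**Step 2. What a pre-post t-test responds to.** The test responds to total change, which is BA effect + effect of DRP care + regression to the mean and other background change. Suppose the BA effect is zero and the rest amounts to d SDs of the change score. The probability of a significant result is P(|T| > t(0.975, n−1)), where T is non-central t with n−1 degrees of freedom and non-centrality d√n. The documents give neither d nor the significance level; a two-sided 5% test and the range of d below are assumptions.

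| Assumed background change d | Non-centrality, n=32 | Significant, n=32 | Non-centrality, n=40 | Significant, n=40 |
|---|---|---|---|---|
| 0 | 0 | 5% | 0 | 5% |
| 0.2 | 1.13 | 20% | 1.26 | 23% |
| 0.3 | 1.70 | 38% | 1.90 | 46% |
| 0.5 | 2.83 | 78% | 3.16 | 87% |

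For any non-zero background change the probability rises with n. A larger sample makes the misreading more likely, so size cannot support the efficacy claim.

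**Step 3. Retention.** Retention in the programme has no baseline value, so Step 2 does not apply to it. The design limit still does: a retention percentage is informative about BA only against what DRP care alone would give, and the plan has no such group. The 80% in section 2d comes from retention in other research at the site and is used there to set enrolment. It is not offered as a benchmark for MOUD retention.

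**Step 4. Precision of percentages based on enrolled patients.** Exact (Clopper-Pearson) 95% limits for x out of n are the 0.025 quantile of Beta(x, n−x+1) and the 0.975 quantile of Beta(x+1, n−x).

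| Observed | Exact 95% CI |
|---|---|
| 32/40 (80%) | 64.4% to 90.9% |
| 30/40 (75%) | 58.8% to 87.3% |
| 20/40 (50%) | 33.8% to 66.2% |
| 26/32 (81%) | 63.6% to 92.8% |
| 16/32 (50%) | 31.9% to 68.1% |

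These apply to acceptability, whose denominator is enrolled patients, and to retention if all enrolled are counted. They do not apply to feasibility, whose denominator is those screened eligible and is not capped at 40, or to fidelity, which counts coded components in 20% of sessions.

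**Step 5. Precision of a mean change.** The 95% CI half-width is t(0.975, n−1)/√n in SDs of the change: 2.04/5.66 = 0.36 for n=32, and 2.02/6.32 = 0.32 for n=40.

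**The case against.** The strongest reply is that this is a pilot and mostly behaves like one. Section 1 calls it a pilot, section 2d says preliminary and gives a formative purpose, and the SAP is descriptive with no efficacy test. Nothing in the plan turns on a threshold, descriptive statistics do not exclude intervals, and any harm depends on a later misreading. Much of this stands. A small sample without a power calculation or success threshold is acceptable in a pilot, and the design can serve the formative purpose. But the word preliminary signals limited certainty; it does not supply a counterfactual. Section 2d still says demonstrate, and section 1 still lists effectiveness as a goal.

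Several stronger readings are tempting, and the documents do not support them:

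- *That the efficacy claim rests on the t-tests alone.* The protocol never calls them efficacy tests and names no outcome for them. Retention is the intervention's stated target and an SAP primary outcome, so the limit must cover it too.
- *That the trial has a 78% chance of a false efficacy finding.* That figure belongs to one assumed background change on an unnamed outcome. The share of participants who are new intakes is also unknown, since section 3 allows contact during routine visits.
- *That every SAP percentage has the interval widths in Step 4.* Feasibility and fidelity have other denominators.
- *That 32 is miscalculated.* It is not.

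**Conclusion.** The concern holds as a wording and reporting fault. Section 2d attributes to the sample a property that the design lacks at any size. That conclusion needs no numerical assumption: it follows from the absence of a comparator and from concurrent DRP treatment, and it covers retention as well as pre-post change.

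The rejection rates of about 20%, 38% and 78% with 32 patients illustrate the risk and rest on the assumed background changes and an assumed two-sided 5% test. The intervals are exact for the counts shown: roughly 64% to 91% around an observed 80% of 40, and 34% to 66% around 50%. The SAP does not ask for such intervals.

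The change should be made, but it does not call the pilot itself into question. The documents also describe eligibility differently with respect to SUD in general and opioid use. That is a separate matter and not part of this point.

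**What to change.** 1. **Protocol section 2d and section 1.** Replace the claim to demonstrate preliminary efficacy with one of estimation, and add a precision statement limited to percentages of enrolled patients. For example: *With 40 enrolled, an observed 80% has an exact 95% CI of about 64% to 91%, and an observed 50% about 34% to 66%; with 32, an observed 50% gives about 32% to 68%. This applies to acceptability, and to retention if all enrolled are counted.* Align the effectiveness goal in section 1 with this wording.
2. **SAP.** Report retention, feasibility and acceptability each with numerator, its own denominator and an exact (Clopper-Pearson) 95% CI. For feasibility the denominator is those screened eligible. Report fidelity with numerator and denominator only, because coded components are clustered within sessions and a simple binomial interval would not be valid.
3. **Protocol section 3, Data analysis, and SAP.** Report both pre-post changes and retention as uncontrolled estimates, with 95% CIs, during DRP treatment plus BA, and say that they are not evidence of efficacy.

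The cost is protocol and SAP wording and a few lines of analysis code, with no extra patients, visits or data collection. The downside is a less favourable stated claim.

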3. STUDY PROCEDURES

Recruitment and Screening:

As stated above, recruitment will take place at the Detroit Recovery Project (DRP). All patients with SUD will be given the opportunity to learn more about this study from DRP staff, who will refer patients to research staff if interested. Patients will be contacted by a member of the research study team by phone, text, email, or in-person (during routine visit to the treatment center) and asked if they are interested in hearing about a study that is testing a new intervention to help people stay in treatment. Interested individuals will also have the opportunity to write their name and contact details on a research study flyer and to deposit this flyer in a secure lockbox for the research team to contact them.

Patients will be informed that the study provides ClinCard compensation, that their participation is voluntary, and that participation has no impact on their treatment at DRP or at any other location.

All DRP patients who present with SUD are referred at intake; for new patients, a small battery of assessments will be integrated into the intake in order to assess eligibility. The baseline will then be finished by a researcher if the potential participant is eligible, interested and consents to participation. After discussing the study with a research team member, and based on patient continued interest, participants will be offered paper copies of the consent form for their records.. Eligible participants who successfully complete the informed consent process will be given a unique identification number. This number will be used in place of their name for the remainder of the study.

Interested, eligible, and consented participants will then be scheduled to complete the Baseline assessment. Baseline measures can include demographic characteristics and history of substance use treatment, measures of treatment adherence, measures of problems related to substance use, substance use frequency and severity, other mental and physical health characteristics, readiness for change, quality of life, social support and current activities. The measures to assess the topics listed above can be found in the Measures document. Please also reference the Intervention Flow Diagram for a visual timeline of measure use. Patients who are deemed ineligible following the full baseline assessment due to lower than moderate opioid use or current psychotic or manic symptoms will be provided additional resources (see Resource List document) and may continue with usual care at the center.

At all stages of recruitment, we will reiterate that participation or non-participation will not influence the patient's treatment, resources, or other relationships with DRP.

Intervention and Assessments:

Following completion of the baseline assessment, the participant can meet with the PRC approximately 8 BA sessions that can be scheduled based on individual treatment plans and particular participant needs, with the aim of a minimum session frequency of every other week. Following treatment completion, participants will be able to schedule up to 4 booster sessions to provide further assistance with addressing barriers to treatment. These sessions will be held either remotely or in-person at the drug treatment center, depending on participant availability and preference. Based on participant needs and preferences, the PRC may provide a second check-in between BA sessions. The additional check-in will focus on challenges and barriers that participants are experiencing in their SU treatment. These sessions can be conducted via phone (including telephone, Zoomvideoconference (Zoom), or in-person at the drug treatment center. Participants can conduct remote sessions from their homes or other preferred private locations. In-person sessions will take place at DRP or other mutually convenient locations and follow all necessary COVID-19 precautions outlined in the approved in-person human subjects research proposal. Participants may also choose to participate in these virtual sessions at DRP during routine visits to the treatment center with the peer at a separate location. These procedures will follow the current telehealth practices and protocols being used at DRP.

The study interventionist will be a trained and supervised PRC who will receive training in protocol and intervention procedures. Supervision sessions between the PRC and DRP clinical supervision staff will take place approximately weekly, with inclusion of key personnel as needed (I.e. Drs. [name], [name] and/or [name]). The supervisor will utilize recordings of intervention sessions while supervising the PRS. The peer hired as the study interventionist will be a Michigan Certified Peer Recovery Specialist (CPRS). CPRS certification is managed by Michigan Department of Health and requires 56 hours of training.

Throughout the treatment program, the PRC will attempt to work with the patient weekly. These sessions will occur in-person or via phone or over Zoom, a cloud-based video-conferencing system which allows for participants to call-in via phone or computer. Call administrators are able to record and store audio from a call on a local drive. Phone sessions will be recorded using Zoom or a hand-held recorder, in-person sessions will be recorded using a hand-held recorder, and all recordings will be saved to UMB Box folder before they are deleted from the recording device. In order to further protect participant privacy, no audio recording will be saved to a cloud platform. Sessions will be audio-recorded for supervision and to assess for treatment fidelity. This is noted in the consent process, and participants can refuse audio-recording at any time (refusal of audio recording does not preclude participants from continuing to be part of the study). The PRC will reiterate before conducting each session that the audio-recording is for research purposes only, will not include any identifiable information, and will be kept confidential. Zoom security functions include a Waiting Room in which individuals can be screened before the call administrator allows them to join the call, and a Lock Meeting function which allows the administrator to block new participants from joining. Depending on different participants' needs, the timing of PRC meetings are expected to vary and will generally last up to half an hour to an approximate maximum of one hour. The PRC role is often flexible, particularly for patients who are poorly engaged in care. We will document how and when sessions take place (method of communication, locations of PRC and participants, time of day) to further our understanding of how the PRC role can optimize participant engagement in treatment.

In order to assess SUD retention and treatment adherence, research staff will extract routinely-collected data from patient medical charts (maintained by DRP) at each BA session and assessment, with collected data consisting of intake date, clinic attendance, counselor appointments, engagement in psychosocial services, any breathalyzer results, any urinalysis or other drug testing results, and, when applicable, MOUD dosing, dose volume and any notes on patient dosing. We will ask participants about any changes to their enrollment in

treatment programs (see Treatment Program Status, MOUD Adherence and Retention: Chart Extraction in Measures document). This use of medical records is outlined in the consent form. At each BA session, participants will complete two items on the Ira Wilson's Self Report Adherence Measure.

During the approximately weekly or biweekly sessions, the PRC will determine the participants' specific circumstances and needs and will draw upon intervention components accordingly. Intervention components can include: Life Steps to identifying and overcoming day-to-day barriers to treatment, SMART goal identification and work, case management with the treatment facility, and modified Behavioral Activation (BA) to support retention in treatment. The PRC will complete/update the intake goals and follow-up goals with the participant during sessions to keep track of the participants' individual plans moving forward. The PRC can also work through BA modules during sessions and review material as needed. After sessions, the PRC will complete a fidelity assessment to indicate which components were addressed (see the Fidelity measure guide in the Measures document). Specifically, the approach can focus on the following six elements: (1) psychoeducation regarding substance use, (2) treatment rationale, (3) identification of treatment barriers and solution planning, (4) identification of valued life areas to guide activity selection, (5) monitoring of current activities, (6) scheduling of new activities, and (7) tracking of actual behaviors and subsequent substance use behaviors.

If a participant misses BA sessions, the PRC will continue to follow up with the participant to assess barriers, concerns, and try to continue treatment.

With participant permission, all sessions will be audio recorded for supervision purposes and for fidelity assessments. A trained, independent rater will review approximately 20% of audio-recordings from sessions. This rater may be a research team member who is located at the University of Maryland, College Park. The independent rater will fill out fidelity measures based on these session recordings for later comparison with the PRC's self-reported fidelity (see Fidelity measure in Measures document).

At the approximately mid intervention and post-intervention, a trained member of the research team will complete remote or in-person (depending on participant availability, COVID-19 protocols, and participant preference) assessments with the participant. We anticipate that phone or video-based assessments may need to be shorter than in-person assessments; thus, we have streamlined and reordered our assessment measures to prioritize the most important measures for this study. This will allow us to gather the most important data earliest during the remote assessments in case a participant experiences difficulty with technology or is unable to continue the remote assessment for some other reason (such as a family emergency). The approximately 6-week midpoint assessment will be a brief assessment of factors that we hypothesize may change during the course of the intervention. Measures that can be used in this assessment are listed in the Intervention Flow document. The post-treatment assessment measures can include the same measures as the baseline assessment with the exception of no Demographic and other Characteristics Questionnaire. The post-treatment assessment can also include the Treatment Program Status form, Working Alliance Inventory Short Revision and the JHU Feasibility and Acceptability measure, to assess the participant's satisfaction with working with the PRC and important barriers and facilitators to implementation of the intervention.

After completing the posttreatment assessment, participants will be invited to complete a qualitative exit interview which will ask them about their experience in the treatment (see Exit Interview Guide). Exit interview can take place by phone, video, or in-person. Participants who have dropped out of the program early will also be invited to complete the midpoint assessment, posttreatment assessment, and exit interview over the remaining period of the planned study timeframe (an intent-to-treat approach) or at their earliest convenience. The exit interview will take place immediately following the posttreatment assessment or may be scheduled

within approximately one week. Because this interview will ask about the participants' experiences with the PRC, the interview will be conducted by a trained member of the study staff and the participants' responses will not be shared with the PRC. The participant will be asked for their consent for the interview to be recorded. They will be assured that audio recording will be used for research purposes only. The recording will be uploaded to UMB's Box folder immediately following the session, and the audio file will be deleted from the recording device.

It will take approximately 30-60 minutes to complete the baseline assessment, approximately 15-30 minutes to complete the midpoint assessment, approximately 30-60 minutes to complete the posttreatment assessment, and approximately 30 minutes to complete the posttreatment exit interview. All compensation for study related activities will be in the form of a reloadable ClinCard. The participant will receive \$10 (ClinCard) for completing the baseline, \$15 for completing the midpoint assessment, a \$25 ClinCard for completing the posttreatment assessment, and \$25 for completing the exit interview. Total compensation for baseline assessment, midpoint assessment, posttreatment assessment, and exit interview will be up to \$75.

We recognize that meeting with participants remotely or in person may both present new challenges to participation, including cost associated with using their own device for session contact or cost of attending sessions when not scheduled for other services at DRP. We also understand that participants may also face additional transportation costs when presenting in-person to the drug treatment center during COVID-19. As such, participants will receive compensation in the form of ClinCards for each session attended to cover transportation and/or telecommunication costs. \$10-25 per session will be provided to participants after each session attended for the duration of the study. We have chosen to incrementally increase compensation as sessions persist in order to encourage long-term retention. Participants will receive \$10 per session for BA 1-2, \$15 per session for BA 3-4, \$20 per session for BA 5-7, and \$25 for BA 8. Total compensation for intervention session attendance (above the compensation for assessment participation) will have a maximum of \$135, reflecting attendance of the 8 sessions.

For any remote call with the participant, the research team will document the participant ID number, researcher name, location of research team member, location of participant, means used (telephone or computer), start and end time, quality of call (excellent, minor issues, significant impediment), and any barriers to effective communication in RedCap. For any in-person session (assessment or intervention session), researchers will follow procedures outlined in the IRB-approved in-person human subjects protocol.

Data analysis:

Quantitative data will involve pre- to-post t-tests and will utilize multiple imputation to handle missing data if deemed appropriate and necessary.

Qualitative data will be analyzed using thematic analysis, and the coding team will iteratively develop a codebook outlining themes, sub-themes, and definitions in the transcripts. The codebook will be modified as new concepts arise.

